Cover Page Protocol and SAP

Official Title of the study: A 14 Week Study of Mindfulness Effects on Attentional Control in Older Adults
(The MACS Study: Mindfulness and Attentional Control in Seniors)

NCT number: NCT02714426

Date of the document: IRB version: 03-30-2016

1. Background:

The proposed study is an intensive micro-longitudinal 14-week investigation exploring week to week changes in attentional and emotional control in older adults who do and do not receive 8-weeks of mindfulness education and training. The study focuses narrowly on attentional and emotional control. The study compares changes in attentional and emotional control between one group of participants who receive fourteen weeks of weekly testing plus eight weeks of mindfulness training and education, and another that receives that receives the same fourteen weeks of testing plus eight weeks of active control 'brain health' educational sessions. The development of this study was guided by several key concepts:

Mindfulness meditation, with its primary focus on attention to the present moment,¹ is one possible avenue for attentional improvement in young and middle-aged adults. A small but steadily growing body of literature suggests that meditation may have similar effects on attentional control in late life, a period of normative decline ^{2,3}. It has been shown that mindfulness meditative practice, such as a standardized mindfulness based stress reduction program (MBSR; Kabat-Zinn, 2003),¹ increases the efficiency of attention networks.^{4,5,6} so applying mindfulness inspired interventions would seem to offer one route to cognitive remediation in older adults.

Additionally, to date, the majority of studies that have related mindfulness meditation practice to attentional control have been based on retrospective self-reported mindfulness or cross-sectional measurement in experienced meditators.^{7,8,9} More recent experimental studies have ventured only to determine that meditation naïve individuals can experience attentional improvement with mindfulness intervention,^{10,11,12} (rather than why) using pre-post mindfulness training designs. The time course of the association of mindfulness training with attention has yet to be studied, leaving a gap in the field's collective knowledge of when and how these improvements manifest.

Finally, although emotion regulation is thought to improve through mindfulness,¹³ the time course of its development and its potential influence on attentional control have thus far been unclear. Therefore, emotion-related data is important to collect with respect to the time course of attentional change.

2. Specific Aims:

The proposed micro-longitudinal research study will consider the relationship between mindfulness meditation practice and attentional control in older age, with a focus on the temporal dynamics of attentional and emotional change produced during 8-weeks of mindfulness sessions. This study, by examining the week-to-week trajectory of gains in an older adult sample undergoing training in mindfulness, will expand our understanding of possible dose-response relationships, as well as possible mediators of those gains, areas for which minimal data exist.

3. Research Plan / Study Description:

Initial Telephone Contact:

Prior to in-person contact with the study, potential participants will first be contacted via telephone.

Exclusion criteria are:

- Under 65 years of age
- Lack of time and willingness to commit to the completion of this 14-week study
- Less than an 8th grade education
- Having been told by a healthcare provider that they
 - Have ever had a major stroke or mini-stroke
 - Have ever had a traumatic brain injury (e.g. moderate to severe brain injury)Have ever had another significant brain abnormality
 - Have a neurodegenerative disorder (Parkinson's disease, Huntington's disease, dementia of any type, etc.)
- Current or past history of major psychiatric disturbance including schizophrenia, or active psychosis, current major depressive episode, current alcohol or substance abuse or history thereof within the past six months, or EVER HOSPITALIZED for any of the above conditions
- Radiation treatment for cancer above the neck
- Extreme difficulty reading ordinary print in a newspaper, or have stopped reading due to poor eyesight.
- Extreme difficulty hearing, or being completely unable to hear, ordinary speech in low-noise conditions, even with hearing aid
- Currently participating in cognitive training or brain training
- Having participated in any cognitive or brain training study within the last 6 months
- Any prior training in (e.g. multi-day course) in mindfulness meditation, or current practice of any form of meditation.
- History of receiving cognitive or neuropsychological testing within the last 6 months

To avoid collecting personal health information, participants will not be asked to report on their status regarding these exclusion criteria individually. Instead, they will be asked to endorse their eligibility based on all the criteria in the single block. This ensures that investigators do not know, and cannot record, which specific exclusion criteria, if any, disqualifies the individual.

If individuals are eligible to take part in the study, they will be scheduled for an intake consent and baseline assessment session.

Consent, Baseline Assessment/Pretest, and Post-test Assessment:

Consent procedures are described below. Baseline assessments will include a demographics questionnaire, a self-administered health comorbidity scale, a global health-related quality of life survey, measures of self-reported everyday function, a measure of global cognition, and a measure of reading literacy (Appendix B).

Participants will also complete emotion, mood, and mindfulness questionnaires, and will complete computerized and paper-and-pencil cognitive testing. Following this initial visit, participants will be randomly assigned to either the active control brain health group or the mindfulness group.

At the Post-test visit, all participants will complete a subset of the same emotion, mood, and mindfulness questionnaires, and cognitive testing measures that were completed at the Consent and Baseline/Pre-test visit. It should be noted that the inclusion of the global cognition measure and mood questionnaires is NOT for clinical case determination/diagnosis or screening. Rather, these measures are being used as brief, well validated measures of individual differences in mood and global cognition, to characterize the sample in manuscripts.

Weeks 1-14

The total anticipated sample has the goal of enrolling 48 individuals who fully complete all study activities. To distribute workload, the study will be conducted in three to four replicates, each enrolling twelve (12) to sixteen (16) participants. For all participants, their personal study participation is 14-16 weeks long (including pre- and post-testing, and includes 1 hour of attentional and emotional control assessment challenges each week for 14 weeks. Participants will also spend an additional 2 hours each week with the study in weeks 4-11 to participate in 8 weekly group sessions (mindfulness or active control 'brain health' education).

Mindfulness Procedure

In the mindfulness program, participants will participate in 8 weekly group sessions, each lasting approximately 2 hours in duration, along with a half day Mindfulness Retreat at the end of the training period. Specific course material will adhere strictly to a manualized protocol by Stahl and Goldstein (2000).¹⁴ A detailed schedule of training session content is outlined in Appendix E. Each session will include 1) a psychoeducational component, 2) formal exercises in the form of guided practice, and 3) thoughtful exploration of ideas and questions. Formal mindfulness practices will follow 21 guided pre-recorded meditative MP3 tracks from the authors for use in class

and at home, promoting both fidelity to the protocol and uniformity across replicates. Activities in the protocol include mindful breathing, eating, walking, and various other practices well documented in the literature to promote mindfulness. Participants will also be asked to practice on their own time and to take note of the amount of practice they complete outside of class.

Active Control Procedure

An active control comparison group will be included in this study. This group will take the form of a health enhancement 'brain health' education program. Topics to be presented and discussed in this group will include healthy sleep, healthy eating, exercise, aging and mental health, dementia risk factors, cognitively stimulating activities, overall safety and health management in older age, and social engagement in late life. Like in the mindfulness program, participants randomized to this active control group will participate in 8 weekly group sessions, each lasting approximately 2 hours in duration. Every effort will be made to keep this group equivalent to the mindfulness group in terms of length of session, participant interaction with each other and with study staff, and other factors like time of day.

Data analysis:

[name], with the assistance of [name], will conduct analyses once data have been collected. Multivariate latent change models (e.g. curve of factors or factors of curves) and dual change score models will be used to examine overall trajectory of global attentional change as well as lead-lag relations between affective and cognitive changes across 14 weeks.

4. Possible Discomforts and Risks:

To the best of our knowledge, the physical, psychological, and social risks associated with this study are less than minimal. However, some participants may experience some frustration or worry about their performance during the attention tasks.

Participants will be encouraged to simply try their best during these tasks. During the testing session, participants will be asked frequently about their level of comfort; if they become uncomfortable, they will be offered as many breaks as they want.

In addition, some participants may feel uncomfortable completing required activities in front of others in the group. Participants are reminded that their participation is voluntary, that they will be randomly assigned to an experimental group, and selecting to opt out of participating will not affect their medical care or residential status at The Village (if applicable) in any way.

There is, as with all research studies, a slight risk that information about participants could be revealed inappropriately or accidentally (e.g., if there is a forced break-in into our locked offices and locked file cabinets). Although we consider such risk to be less than minimal, depending on the nature of the information, such a release could upset or embarrass participants.

5. Possible Benefits:

There is no guaranteed direct benefit to participants. Repeated re-testing over 14 weeks has been shown in many studies to result in practice-related improvement. Therefore, many participants may be expected to experience improved cognitive scores. In addition, given that mindfulness meditation therapies have been effective at improving mood and coping, some participants may experience mood benefits that would include decreased symptoms of depression, apathy, anxiety, and perceived stress.

6. Conflict of Interest:

No financial or ethical conflicts of interest exist or are anticipated by any investigator.

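### Both arms are taught in interactive session groups, yet the analysis states no allowance for session group; if people in a group change alike, a single-level fit understates the arm contrast's standard error unless shared replicate variance is about 6.7 to 10.5 times as large

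*Combined protocol and SAP*

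**What the plan says.** All references are to section 3 of the combined protocol and SAP unless stated.

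- **Randomisation** (Consent, Baseline Assessment/Pretest, and Post-test Assessment): after the first visit, "participants will be randomly assigned to either the active control brain health group or the mindfulness group". Individuals are the unit; no allocation ratio is given.
- **Delivery** (Weeks 1-14): during weeks 4 to 11 everyone is to "participate in 8 weekly group sessions (mindfulness or active control" education). Sessions last about two hours.
- **Layout** (Weeks 1-14): "the study will be conducted in three to four replicates, each enrolling twelve (12) to sixteen (16) participants", with "the goal of enrolling 48 individuals who fully complete all study activities". The number of session groups per arm in a replicate is not stated.
- **Interaction** (Active Control Procedure): the arms are to be kept alike in "length of session, participant interaction with each other and with study staff, and other factors like time of day". Section 4 adds that some people may be uneasy doing the required activities in company.
- **Standardisation** (Mindfulness Procedure): "Specific course material will adhere strictly to a manualized protocol", and recorded tracks are used, "promoting both fidelity to the protocol and uniformity across replicates". This is described for the mindfulness arm only.
- **Analysis** (Data analysis): "Multivariate latent change models (e.g. curve of factors or factors of curves) and dual change score models will be used" to describe the attentional trajectory and the lead-lag relation between affect and cognition. No multilevel form, session-group or replicate term, cluster correction or small-sample degrees of freedom is stated.

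The between-arm comparison of change is stated in section 1. Section 2 puts the focus on time course, dose-response and mediators.

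**The concern.** People who share a room, peers and staff for eight weeks may come to change alike. Randomising individuals does not prevent this, because the correlation arises after allocation. Session groups lie wholly within an arm, so any group effect goes straight into the difference between arms. A single-level model counts 48 independent people, whereas the contrast may rest partly on 6 to 8 groups.

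The arm contrast is also what separates a training effect from the retest gains that section 5 expects in many participants. If its interval is too narrow, differences between session groups could be credited to mindfulness.

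**Working it through.** **Inputs from the documents.** 48 completers; three to four replicates of 12 to 16; group delivery in both arms. The plan's figure agrees with its layout: 3 x 16 = 48 and 4 x 12 = 48. No power calculation is given, so nothing further can be reproduced.

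**Assumed, because the documents are silent.** 1:1 allocation within each replicate; one session group per arm per replicate, so m = 8 (R = 3) or m = 6 (R = 4); no dropout; equal ICC in both arms; a two-sided 5% test on one change score per person.

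**Model.** Change = arm + replicate + session group + person, with variance shares r, g and e that sum to 1. In this step ICC means g, a share of total variance.

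- True variance of the arm difference: (2/R)(g + e/m). Replicate cancels.
- Expected single-level variance: (2/(Rm))[e + (r + g)m(R-1)/(Rm-1)].

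Setting these equal gives g(Rm-1) = (r + g)(R-1), so the break-even is g = r(R-1)/(R(m-1)).

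- 3 x 16: factor 2/(3 x 7) = 0.095, so r must be 10.5 times g.
- 4 x 12: factor 3/(4 x 5) = 0.15, so r must be 6.67 times g.

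At replicate shares of 10% and 20%, the break-even ICC is 0.010 and 0.019 (3 x 16) or 0.015 and 0.030 (4 x 12).

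**Numbers at g = 0.05, r = 0.**

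- 3 x 16: true SE = sqrt[(2/3)(0.05 + 0.95/8)] = 0.335; single-level SE = sqrt[(2/24)(0.95 + 0.05 x 8 x 2/23)] = 0.286 to 0.287; ratio 0.85.
- 4 x 12: true SE = sqrt[(2/4)(0.05 + 0.95/6)] = 0.323; single-level SE = sqrt[(2/24)(0.95 + 0.05 x 6 x 3/23)] = 0.287; ratio 0.89.

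**Simulated type I error (%), two-sample t test with 46 df and no group or replicate term (400,000 null trials per cell).**

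| Replicate share | Layout | ICC 0 | 0.01 | 0.02 | 0.05 | 0.10 |
|---|---|---|---|---|---|---|
| 0 | 3 x 16 | 5.0 | 5.8 | 6.7 | 9.2 | 13.5 |
| 0 | 4 x 12 | 5.0 | 5.5 | 6.2 | 8.0 | 11.1 |
| 10% | 3 x 16 | 4.3 | 5.2 | 6.0 | 8.6 | 13.2 |
| 10% | 4 x 12 | 4.2 | 4.7 | 5.3 | 7.2 | 10.4 |
| 20% | 3 x 16 | 3.6 | 4.5 | 5.4 | 8.1 | 13.0 |
| 20% | 4 x 12 | 3.4 | 4.0 | 4.6 | 6.5 | 9.8 |

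**Two session groups per arm per replicate**, at replicate share 0 / 10 / 20%: ICC 0.05 gives 6.8 / 6.1 / 5.5% (groups of 4) and 6.3 / 5.4 / 4.6% (groups of 3). ICC 0.10 gives 8.6 / 8.1 / 7.4% and 7.3 / 6.6 / 5.9%.

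**Closer to the planned models.** In a single-level linear latent growth model with arm on slope and a maximum-likelihood z test, replicate share 0, type I error at ICC 0 / 0.05 / 0.10 is 6.1 / 10.8 / 15.4% (3 x 16) and 6.1 / 9.4 / 12.9% (4 x 12). The 6.1% at ICC 0 is a small-sample effect, not clustering. Here ICC refers to the per-person estimated slope.

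**Adding replicate alone** makes matters worse, because it removes the offset. At replicate share 20%, ICC 0.05 goes from 8.1 to 10.6% (3 x 16) and from 6.5 to 9.1% (4 x 12). ICC 0.10 goes from 13.0 to 16.6% and from 9.8 to 13.5%.

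**The case against.** Four points deserve weight.

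1. **Silence is not a single-level assumption.** The plan names model families, with an e.g., and gives no estimator or covariates. A reader might infer that the plan assumes independence. The documents do not say so and do not rule out a multilevel fit. What stands is that no allowance is stated; the conclusion is conditional on the ordinary single-level form.
2. **The computed test is not in the plan.** The analysis sentence concerns trajectory and lead-lag relations, and no confirmatory test or alpha is named. That is so, but section 1 states the arm comparison, and the variance argument carries over to an arm effect on a latent slope. It does not show that the lead-lag estimates are wrong, and no such claim is made.
3. **The ICC is unknown and may be low.** The manual, recorded tracks and home practice favour a low value in the mindfulness arm, and shared sessions cover only 8 of 14 weeks. A reader might take 13.5% as the trial's error rate; no document supports that or any particular ICC. Nor does a positive ICC alone settle the direction: results in the table run from 3.4 to 13.5%. Standardised material still does not show that group variance is zero.
4. **Replicate is not the culprit.** A reader might blame the missing replicate term. Omitting it works the other way.

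**Conclusion.** The concern holds in conditional form. Group delivery with interaction in both arms is stated, and no allowance for session group is. In a single-level fit, the arm contrast's standard error is too small on average once session-group variance passes a low break-even: about 0.10 (3 x 16) or 0.15 (4 x 12) of the replicate variance. Replicate variance merely larger than session-group variance is not enough to offset the problem.

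The size cannot be known from the documents. It rests on the assumed ICC, 1:1 allocation, number of session groups, equal ICC across arms and single-level fitting. With two groups per arm per replicate it is clearly smaller. This is a cheap improvement of modest severity, not a fault that invalidates the design.

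**What to change.** 1. Record replicate and session-group ID for every participant.
2. Alongside the latent change models, report the arm contrast on each person's change or training-phase slope, with replicate as a fixed effect and an explicit session-group allowance: Var(diff) = (2/(Rm)) x s2_within x (1 + (m-1)ICC)/(1-ICC), on 2R(m-1) degrees of freedom (42 for 3 x 16, 40 for 4 x 12). Here s2_within is the pooled variance within session groups, and ICC = session-group variance / (session-group + residual variance), conditional on replicate and assumed equal in both arms. Use 0, 0.02, 0.05, 0.10 and 0.15. The grid runs to 0.15 because an ICC of 0.10 of total variance at replicate share 20% is 0.10/0.80 = 0.125 on this scale. Treat the ICC 0 row as a reference only, and do not add replicate without the session-group allowance.
3. As a check that needs no assumed ICC, report session-group means paired within replicate (R-1 = 2 or 3 df). This held 4.8 to 5.2% in every scenario simulated. Do not rely on large-sample cluster-robust errors with 6 to 8 groups.
4. State that the single-level latent change and lead-lag estimates are not adjusted for session group.

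**Cost.** Two stored fields, a little extra analysis and wider intervals. In SDs of change after removing replicate, the mean 95% half-width is 0.56 to 0.58 for the single-level model with replicate. At a correctly assumed ICC of 0.02 / 0.05 / 0.10 it is 0.618 / 0.673 / 0.755 (3 x 16) or 0.608 / 0.648 / 0.710 (4 x 12). The paired check is imprecise: at ICC 0.05 its mean half-width is the t quantile x the mean of s/sigma x the true SE, i.e. 4.303 x 0.886 x 0.335 = 1.28 (3 x 16) or 3.182 x 0.921 x 0.323 = 0.95 (4 x 12).

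A wrong assumed ICC still misstates the error. With true ICC 0.05, type I error is 7.5 / 6.9% (3 x 16 / 4 x 12) if 0.02 is assumed and 2.5 / 2.8% if 0.10 is assumed. That is why the whole range should be shown.

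### Do 28 or more weekly variables on 48 people invalidate the tests from the planned latent change models?

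*Combined protocol and SAP*

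**What the plan says.** The Data analysis paragraph of section 3 has one substantive sentence. It names "Multivariate latent change models (e.g. curve of factors or factors of curves) and dual change score models" for two purposes: the course of attention overall, and "lead-lag relations between affective and cognitive changes across 14 weeks".

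The data come from the Weeks 1-14 paragraph of the same section. Each person's participation "includes 1 hour of attentional and emotional control assessment challenges each week for 14 weeks". The sample is a "goal of enrolling 48 individuals who fully complete all study activities", and "the study will be conducted in three to four replicates, each enrolling twelve (12) to sixteen (16) participants". After baseline, "participants will be randomly assigned to either the active control brain health group or the mindfulness group".

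The plan does not give:
- the allocation ratio;
- the number of weekly indicators per domain;
- whether arms are fitted together or separately;
- the estimator;
- any fit test, likelihood-ratio test, significance level or rule for choosing between models.

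**The concern.** A latent change model over 14 weeks treats each weekly score as a separate variable. Two domains give at least 28 variables, and a curve-of-factors model with two indicators per domain gives 56. Against 24 people per arm, or 48 in all, the sample covariance matrix is singular or close to it. Chi-square reference distributions for structural equation models are large-sample results, so every p-value from such a model looks suspect.

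Two harms would follow if that were so. Correct models would fail their fit test, which could prompt respecification after seeing the data. And affect-to-attention coupling could be declared significant too often. The second is the serious one, because section 2 aims to describe how attentional and emotional change unfold and what might mediate the gains.

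**Working it through.** **The plan's own figure.** No power or precision calculation lies behind 48. It agrees with the replicate plan (3 × 16 = 48 or 4 × 12 = 48), whose limits are 3 × 12 = 36 and 4 × 16 = 64.

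**Variable counts.** With *a* attention and *b* affect indicators per week, p = 14 × (a + b).

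| Model | p | Above 24? | Above 48? |
|---|---|---|---|
| Attention only, one score | 14 | no | no |
| One score per domain | 28 | yes | no |
| Two plus one | 42 | yes | no |
| Two plus two | 56 | yes | yes |
| Three plus three | 84 | yes | yes |

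So variables outnumber people at the 28-variable minimum only if arms are fitted separately and allocation is 1:1 (48 / 2 = 24). They exceed the pooled 48 only with four or more weekly indicators across the two domains.

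**Two kinds of test.** The distinction decides the point.
- Global fit: T = 2[ℓ(saturated) − ℓ(model)]. The saturated term contains log|S|, where S is the sample covariance matrix. The rank of S is at most n − 1, so in an arm of 24 it is 23, below 28. Then |S| = 0 and T is undefined. Pooled, 47 exceeds 28 and T exists.
- Nested comparison: T = 2[ℓ(larger model) − ℓ(smaller model)]. Both terms come from structured models, the saturated term cancels, and a singular S does no direct harm.

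**Simulation inputs (assumed, since the plan gives none).** Bivariate dual change model; 14 weeks; one score per domain; 24 per arm; normal data with no dropout; maximum likelihood; self-feedback −0.1 in each process; true coupling zero; no arm effect. Parameters: 4 dynamic + 4 means + 10 latent covariance + 3 residual = 21. Degrees of freedom for global fit: 28 × 29 / 2 + 28 − 21 = 406 + 28 − 21 = 413.

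**Results, nominal 5%.**

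| Test | Sample | Data sets | Rejects a true null |
|---|---|---|---|
| Global fit, 413 df | 48 | 800 | 98.8% (mean T = 548) |
| Coupling, 1 df | 48 | 800 | 6.6% |
| Coupling, 2 df | 48 | 800 | 6.5% |
| Arm effect on attention slope, 1 df | 48 | 800 | 5.8% |
| All 21 parameters equal across arms | 48 | 800 | 9.4% |
| Coupling, 1 df | one arm, 24 | 1000 | 6.7% |
| Coupling, 2 df | one arm, 24 | 1000 | 5.8% |

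The Monte Carlo standard error at 5% with 800 data sets is √(0.05 × 0.95 / 800) = 0.8 points; at 9.4% it is 1.0. The global fit failure is plain from the mean: the 5% critical value on 413 df is about 413 + 1.645 × √826 ≈ 460, well below 548.

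**Sensitivity.**
- Testing a fully specified true covariance (406 df, 1500 runs each) gives the same picture for global fit: about 98% rejection for 28 variables at N = 48, 82% at N = 64, and 100% at N = 36.
- The one-parameter coupling test under other assumed variances and dynamics gave 5.6%, 3.9% and 4.6% at N = 48 (about 500 runs each), 6.4% at N = 24 and 6.0% at N = 480. Smaller sets of runs gave between 2% (150 runs) and 6.5% (200 runs) at N = 48, and 6.5% and 7% at N = 24.

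**The case for a change.** The strongest opposing evidence is a simulation of the coupling test that rejected a true null in 20% of 161 trials at N = 48 (standard error 3 points). The same program gave 11% (standard error 3 points) at N = 480. There, people outnumber the 28 variables by 480 / 28 ≈ 17 to 1, so scarcity of people cannot explain the excess. If the restricted model stops short of its maximum, the statistic is inflated at any sample size, and incomplete optimisation is the likely cause. Separate fits with analytic gradients and refitting from alternative starts gave 5.6% at N = 48 and 6.0% at N = 480. The 20% does not stand.

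Three things do stand:
- The uncorrected global fit test is useless at this size. An analyst who relied on it would discard correct models.
- Tests of many parameters at once are moderately liberal (9.4% on 21 df).
- The plan is terse. Stating the weekly indicators, pooled or multi-group fitting, and a small-sample way to judge fit would make it easier to follow.

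The evidence also has limits. Models with 56 or 84 variables, non-normal scores, missing weeks and clustering by session group were not simulated, and some fits started from the true values.

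**Conclusion.** No change to the plan follows. The count of 28 is right for a bivariate model, and the global chi-square test fails at this size (98.8% false rejection pooled, undefined in an arm of 24). But the plan does not rest any conclusion on that test. The low-dimensional tests that would address lead-lag relations and the arm difference stay near nominal, about 2% to 7% against 5%, even in a single arm where variables outnumber people.

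What remains is unstated detail that analysts ordinarily settle when they fit such models: which indicators to use, whether to pool the arms, and how to judge fit in a small sample.

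The larger alternatives offer little clear gain:
- Replacing the measurement model with weekly composites and a mixed model gives up the latent structure the investigators chose. That is a trade-off.
- Bootstrapping the coupling test would correct an error of roughly two percentage points at most.
- Labelling the lead-lag results exploratory adds little, since section 1 already presents the study as an exploration of weekly change.

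This rests on normal data, complete follow-up, one score per domain per week, and 1:1 allocation for the per-arm figures. None of these is stated in the plan.
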